#### Protein bound:

XL184 is highly protein bound ( $\geq 99.9\%$ ). Use caution when coadministering XL184 with medications that are highly protein-bound (e.g., diazepam, furosemide, dicloxacillin, and propranolol). Avoid administration of warfarin with XL184 as warfarin is highly protein-bound and has a very narrow therapeutic index.

#### Antacids, H2-blockers, PPIs:

Co-administration of gastric pH modifying drugs such as PPI, H2-blockers or antacids has no clinically-relevant effect on XL184 plasma PK in healthy volunteers; thus, concomitant use of these drugs with XL184 is allowed.

QTc prolongation: Use caution when administering XL184 in patients with QT prolongation risk, a history of QT interval prolongation, or who are receiving antiarrhythmic drugs. Concomitant use of strong CYP3A4

inhibitors should be avoided as it may increase XL184 plasma concentrations. Refer to the protocol for QTcF criteria.

#### **5.4 Duration of Therapy**

In the absence of treatment delays due to adverse event(s), treatment may continue until one of the following criteria applies:

- Disease progression,
- Intercurrent illness that prevents further administration of treatment,
- Dose-limiting toxicity (DLT requiring discontinuation of therapy, as defined in [Section 5.2](#)). Dose reductions in the first cycle of therapy for cabozantinib-related adverse events are permitted.
- Other unacceptable adverse event(s),
- Treatment delay of 14 days or greater during Cycle 1 due to unresolved toxicity (DLT definition, [Section 5.2](#)).
- Treatment delay in subsequent cycles > 6 weeks due to toxicity (treatment delays for other reasons may be permitted at the discretion of the Study Chairs),
- Participant decides to withdraw from the study.
- General or specific changes in the participant's condition render the participant unacceptable for further treatment in the judgment of the investigator, including:
  - Necessity for treatment with other anticancer treatment prohibited by the protocol.
  - Change to a ritonavir or cobicistat-containing antiretroviral regimen for a participant enrolled on a different study arm (see [Section 5.3.1.2](#)).
  - Sexually active participants who refuse to use medically accepted barrier methods of contraception (e.g., male condom, female condom) during the course of the study and for 6 months following discontinuation of study treatment.
  - Women who become pregnant or are breastfeeding.
- Request by regulatory agencies for termination of treatment of an individual participant or all participants under the protocol.
- Significant noncompliance with the protocol schedule in the opinion of the investigator.
- The minimum dose of study treatment for Stratum A will be the Dose Level -1 dose, and the lowest dose of study treatment for Stratum B and Stratum C will be the Dose Level -2 dose. Participants who cannot tolerate the lowest Dose Level dose for the specified study Stratum will have study treatment discontinued.

#### **5.5 Duration of Follow Up**

Participants will be followed for 30 days after removal from study or until death, whichever occurs first. Participants removed from study for unacceptable adverse event(s) will be followed until resolution or stabilization of the adverse event.

## **5.6 Criteria for Removal from Study**

Participants will be removed from study when any of the criteria listed in [Section 5.4](#) applies. The reason for study treatment removal and the date the participant was removed must be documented in the Off Protocol Treatment Form in AdvantageEDC.

## 6.0 DOSING DELAYS/DOSE MODIFICATIONS

### Dose modifications for Cabozantinib (XL184)

Toxicities warranting treatment delays and dose modifications, along with supportive care guidelines, are noted below.

Stratum-based dose de-escalation of cabozantinib will be permitted for participants experiencing specified toxicity when treated at a particular dose level, as noted below; reductions will be at one-dose-level increments. In no case will dose de-escalation occur beyond the lowest specified Dose Level dose for a particular Stratum (Dose Level -1 for Stratum A; Dose Level -2 for Stratum B and Stratum C). Dose reductions are permanent. No intra-participant dose escalation will be permitted.

**NOTE: Dose modification during Cycle 1 WILL be permitted.** Participants will be permitted to continue study therapy provided no other criteria for protocol discontinuation apply ([Section 5.4](#)). **HOWEVER, treatment delay of 14 days or longer due to unresolved toxicity during Cycle 1 will require discontinuation of study treatment** ([Section 5.4](#)).

**NOTE:** If a participant experiences several adverse events and there are conflicting recommendations, the investigator should use the recommended dose adjustment that reduces the dose to the lowest level.

**NOTE:** Starting in Cycle 2, if toxicity requiring treatment delay does not resolve in less than or equal to 6 weeks, the study treatment will be discontinued. Treatment delays for other reasons may be permitted at the discretion of the Study Chairs.

Dose De-Escalation Schedule			
Dose Level	Dose of Cabozantinib (XL184)*		
	Stratum A ART Regimens Including Drugs that Inhibit CYP3A4 A (mg/day)	Stratum B ART Regimens Including Drugs that Induce CYP3A4 B (mg/day)	Stratum C All Other ART Regimens C (mg/day)
Level -2	-	20	20
Level -1	20 mg every other day	40	40
Level 1	20	60	60
Level 2	40	100	-
Level 3	60	-	-

\* Cabozantinib (XL184) must be taken whole and on an empty stomach. Participants must fast for 2 hours before and 1 hour following each dose of cabozantinib (XL184). To permit pharmacokinetic sampling studies, AM dosing is required during the first cycle of therapy.

AStratum A: Participants taking either ritonavir-boosted or cobicistat-boosted ART regimens

BStratum B: Participants taking either efavirenz or etravirine-based ART regimens.

CStratum C: Participants taking any antiretrovirals not specified in Stratum A or B as of November 30, 2012, and participants who are not taking an ART regimen.

Note: if an antiretroviral is FDA-approved after November 30, 2012, consult the Study

## **6.1 Cabozantinib (XL184)-Related Adverse Event Management**

Participants will be monitored continuously for AEs throughout the study. Participants must be instructed to notify their physician immediately for any and all toxicities.

General guidelines for the management of non-hematologic and hematologic toxicities are provided in [Table 6-1](#) and [Table 6-2](#), respectively. As a general approach, it is suggested that all AEs be managed with supportive care when possible at the earliest signs of toxicity. Calcium, magnesium, potassium, and phosphorus should be kept above the lower limits of the laboratory normal values. For more specific guidelines on gastrointestinal AEs (diarrhea, nausea/vomiting, stomatitis/mucositis), hepatobiliary disorders, pancreatic disorders including lipase and amylase elevations, skin disorders (PPE), embolism and thrombus, hypertension, proteinuria, hemorrhage, rectal and perirectal abscess, gastrointestinal (GI) perforation and GI fistula, non-GI fistula, wound healing and surgery, osteonecrosis of the jaw (ONJ), endocrine disorders and management of treatment-emergent prolongation of the QTc interval, refer to the appropriate below. Guidance for the management of fatigue, anorexia, weight loss, eye disorders, musculoskeletal and connective tissue disorders, nervous system disorders, respiratory/thoracic/mediastinal disorders and congenital, familial and genetic disorders can be found in the Cabozantinib Investigator's Brochure.

*Table 6-1. General Approach to the Management of Cabozantinib-Related Non-Hematologic Adverse Events*

CTCAE Version 5.0 Grade	Guidelines/Intervention
Grade 1:	Add supportive care as indicated. Continue cabozantinib at the current dose level.
Grade 2:	
Grade 2 AEs considered related to cabozantinib that are subjectively tolerable or easily managed	Add supportive care as indicated. Continue cabozantinib at the current dose level.
Grade 2 AEs considered related to cabozantinib that are intolerable to the subject or deemed unacceptable in the investigator's judgment; or are not easily managed or corrected	Interrupt cabozantinib treatment or dose reduction. Add supportive care as indicated. If cabozantinib dosing is interrupted, then upon resolution of the AE to baseline or Grade $\leq 1$ , cabozantinib may be resumed at either the same dose or with a dose reduction at the discretion of the investigator unless this is a recurring event at which time the dose should be reduced.
Grade 3:	
Grade 3 AEs considered related to cabozantinib which occurred without	

• Interrupt cabozantinib and add supportive care as indicated.

• For AEs that are easily managed (e.g., correction of

*Table 6-1. General Approach to the Management of Cabozantinib-Related Non-Hematologic Adverse Events*

CTCAE Version 5.0 Grade	Guidelines/Intervention
optimal prophylaxis or which is easily managed by medical intervention or resolved quickly	
electrolytes) with resolution to baseline or Grade <math>\leq 1</math> within 24 hours, cabozantinib may be resumed at either the same dose or with a dose reduction at the discretion of the investigator unless this is a recurring event at which time the dose should be reduced.
 
 
For AEs that require supportive care, the dose should be held while supportive care is initiated and optimized. Then upon resolution of the AE to baseline or Grade <math>\leq 1</math>, cabozantinib may be resumed at either the same dose or with a dose reduction at the discretion of the investigator unless this is a recurring event at which time the dose should be reduced by ONE dose level.
 

Grade 3 AEs considered related to study treatment that occurred despite optimal prophylaxis or is not easily managed by medical intervention	Interrupt study treatment until recovery to $\leq$ Grade 1 or baseline, and resume treatment with a dose reduction by ONE dose level.
Grade 4:	
Grade 4 AEs considered related to study treatment	Permanently discontinue study treatment unless determined that the subject is unequivocally deriving clinical benefit. In this case, upon recovery to Grade $\leq 1$ or baseline, the subject may be retreated at a reduced dose that is to be determined with Study Chair approval.

With the exception of the first cycle of therapy, dose reductions or delays may occur in the setting of lower grade toxicity than defined above if the investigator believes that it is in the interest of the subject's safety.
	

*Table 6-2. General Approach to the Management of Cabozantinib-Related Hematologic Adverse Events*

CTCAE Version 5.0 Grade	Intervention
Neutropenia	
Grade 3 neutropenia with documented infection	Interrupt cabozantinib treatment until resolution to Grade $\leq 1$ and resume cabozantinib treatment at ONE reduced dose level.
Grade 3 neutropenia $\geq 5$ days	
Grade 4 neutropenia	
Thrombocytopenia	
Grade 3 thrombocytopenia with clinically significant bleeding or	Interrupt cabozantinib treatment until platelet count is $\geq 100,000/\text{mm}^3$ and resume cabozantinib treatment at ONE reduced dose level.

*Table 6-2. General Approach to the Management of Cabozantinib-Related Hematologic Adverse Events*

CTCAE Version 5.0 Grade	Intervention
Grade 4 thrombocytopenia	
Febrile Neutropenia	
Grade 3 febrile neutropenia	Interrupt cabozantinib treatment until recovery of ANC to Grade $\leq 1$ and temperature to $\leq 38.0^{\circ}\text{C}$ and resume cabozantinib treatment at ONE reduced dose level.
Grade 4 febrile neutropenia	Permanently discontinue study treatment unless determined that the subject is unequivocally deriving clinical benefit. In this case, upon recovery to Grade $\leq 1$ or baseline, the subject may be re-treated at a reduced dose that is to be determined with Study Chair approval.
Other Grade 4 Hematologic Toxicities	
Grade 4 hematologic toxicities other than anemia	Permanently discontinue study treatment unless determined that the subject is clearly deriving clinical benefit. In this case, upon recovery to Grade $\leq 1$ or baseline, the subject may be re-treated at a reduced dose that is to be determined with Study Chair approval.
Grade 4 anemia	Permanent discontinuation for Grade 4 anemia is not mandated. Dose reductions or dose delays for anemia should be applied as clinically indicated. Supportive care such as red blood cell transfusions should be managed according to institutional guidelines.

 
• ANC, absolute neutrophil count; LLN, lower limit of normal
 
• Neutropenia: Grade 1 (ANC <math><\text{LLN} - 1.5 \times 10^9/\text{L}</math>); Grade 2 (ANC <math><1.5 - 1.0 \times 10^9/\text{L}</math>), Grade 3 (ANC <math><1.0 - 0.5 \times 10^9/\text{L}</math>), Grade 4 (ANC <math><0.5 \times 10^9/\text{L}</math>).
 
• Febrile Neutropenia: Grade 3 (present); Grade 4 (Life-threatening consequences; urgent intervention indicated).
 
• Thrombocytopenia: Grade 1 (Platelet count <math><\text{LLN} - 75 \times 10^9/\text{L}</math>); Grade 2 (Platelet count <math><75.0 - 50.0 \times 10^9/\text{L}</math>); Grade 3 (Platelet count <math>\leq 50 - 25 \times 10^9/\text{L}</math>); Grade 4 (Platelet count <math>< 25 \times 10^9/\text{L}</math>).
 
	

### 6.1.1 Diarrhea, nausea, vomiting, stomatitis, and mucositis

#### Diarrhea

Participants should be instructed to notify their physician immediately at the first signs of poorly formed or loose stool or an increased frequency of bowel movements. Administration of antidiarrheal agents is recommended at the first sign of diarrhea as initial management. Loperamide is recommended as standard first line therapy. Alternatively, diphenoxylate/atropine can be used. Additional agents to consider in participants with diarrhea that is refractory to the above include deodorized tincture of opium and octreotide (Benson *et al.*, 2004). Some participants may require concomitant therapy with loperamide, diphenoxylate/atropine, and deodorized tincture of opium to control diarrhea. The

dose modification guidance in [Table 6-1](#) should be followed. In addition, general supportive measures should be implemented including continuous oral hydration, correction of fluid and electrolyte abnormalities, small frequent meals, and stopping lactose-containing products, high fat meals, and alcohol.

#### *Nausea and vomiting*

Anti-emetic agents along with supportive care are recommended as clinically appropriate at the first sign of nausea and vomiting. The dose modification guidance in [Table 6-1](#) should be followed.

The 5-HT3 receptor antagonists are recommended over chronic use of NK-1 receptor antagonists and dexamethasone (NK-1 receptor antagonists can induce or inhibit CYP3A4, and glucocorticoids induce CYP3A4 and thus could lower cabozantinib exposure. Caution is also recommended with the use of nabilone, which is a weak inhibitor of CYP3A4. Please also refer to [Appendix IX](#) for antiemetics to be avoided due to potential for QTc prolongation.

#### *Stomatitis and mucositis*

Preventive measures may include a comprehensive dental examination to identify any potential complications before study treatment is initiated. Appropriate correction of local factors should be instituted as indicated, such as modification of ill-fitting dentures and appropriate care of gingivitis. During treatment with cabozantinib, good oral hygiene and standard local treatments such as non-traumatic cleansing, and oral rinses (e.g., with a weak solution of salt and baking soda) should be maintained. The oral cavity should be rinsed and wiped after meals, and dentures should be cleaned and brushed often to remove plaque. Local treatment should be instituted at the earliest onset of symptoms. When stomatitis interferes with adequate nutrition and local therapy is not adequately effective, dose reduction or temporary withholding of cabozantinib should be considered.

#### 6.1.2 Hepatobiliary disorders

Elevations of transaminases have also been observed during treatment with cabozantinib. In general, it is recommended that participants with elevation of ALT, AST, and/or bilirubin have more frequent laboratory monitoring of these parameters. If possible, hepatotoxic concomitant medications and alcohol should be discontinued in participants who develop elevated transaminases.

Since participants may enter the study with elevations of AST/ALT at baseline, the following guideline should be used for dose modifications:

Transaminase Elevation CTCAE v5.0	Intervention
Subjects with AST and ALT less than or equal to the ULN at baseline	
Grade 1	
Continue cabozantinib with weekly monitoring of liver function tests (LFTs) for at least 4 weeks. Then resume the standard protocol-defined monitoring of LFTs.
 
NOTE: Participants remaining with G1 AST/ALT changes following this initial weekly monitoring may continue monitoring every 4 weeks per protocol and when clinically indicated.

Grade 2	
Continue cabozantinib with at least twice weekly monitoring of LFTs for 2 weeks. Then weekly for 4 weeks. If LFTs continue to rise within Grade 2, interrupt cabozantinib treatment. Then continue with at least weekly LFTs until resolution to Grade <math>\leq</math> 1. Study treatment may then be resumed at a one-dose-level reduction of cabozantinib.

Grade 3	
Interrupt cabozantinib treatment and monitor with at least twice weekly LFTs until Grade <math>\leq</math> 2. Then continue with at least weekly LFTs until resolution to Grade <math>\leq</math> 1. Cabozantinib may then be resumed at a one-dose-level reduction.

Grade 4	
Discontinue study treatment permanently. LFTs should be monitored as clinically indicated, at least 2-3 times per week, until resolution to Grade <math>\leq</math> 1. If the subject was unequivocally deriving clinical benefit, the subject may be able to resume treatment at a lower dose of cabozantinib as determined with Study Chair approval.

Subjects with AST or ALT above the ULN but <math>\leq</math> 3.0 x ULN (i.e., Grade 1) at baseline	
<math>\geq</math> 1.5 fold increase of AST or ALT AND both AST and ALT are <math>\leq</math> 5.0 x ULN	
Continue cabozantinib treatment with at least twice weekly monitoring of LFTs for 4 weeks and weekly for 4 weeks. If LFTs continue to rise, interrupt study treatment. Then continue with at least weekly LFTs until resolution to Grade <math>\leq</math> 1. Study treatment may then be resumed at a one-dose-level reduction of cabozantinib.

<math>\geq</math> 1.5 fold increase of AST or ALT and at least one of AST or ALT is Grade 3 (i.e. AST or ALT <math>></math> 5.0 but <math>\leq</math> 20.0 x ULN)	
Interrupt study treatment and monitor with at least twice weekly LFTs until Grade <math>\leq</math> 2. Then continue with at least weekly LFTs until resolution to Grade <math>\leq</math> 1. Study treatment may then be resumed at a one-dose-level reduction of cabozantinib.

Grade 4	
Discontinue study treatment permanently. LFTs should be monitored as clinically indicated, at least 2-3 times per week, until resolution to Grade <math>\leq</math> 1. If the subject was unequivocally deriving

	clinical benefit, the subject may be able to resume treatment at a lower dose as determined with Study Chair approval.
--	--

Cabozantinib treatment should also be interrupted when transaminase increases are accompanied by progressive elevations of total bilirubin, and/or elevations of coagulation tests (e.g., International Normalized Ratio [INR]). Monitoring of transaminases should be intensified (2–3 times per week) and cabozantinib should be held until the etiology of the abnormalities is determined and these abnormalities are corrected or stabilize at clinically acceptable levels (INR < 1.5 × ULN, total bilirubin < 1.5 × ULN, aminotransferases ≤ baseline grade).

Participants must have cabozantinib permanently discontinued if transaminase elevations are accompanied by evidence of impaired hepatic function (bilirubin elevation >2 ×ULN), in the absence of evidence of biliary obstruction (i.e., significant elevation of alkaline phosphatase) or some other explanation of the injury (e.g., viral hepatitis, alcohol hepatitis), as the combined finding (i.e., Hy's Law cases) represents a signal of a potential for the drug to cause severe liver injury.

All participants who develop isolated bilirubin elevations of Grade 3 should have study treatment held until recovered to Grade ≤1 or baseline (or lower). If this occurs within 3 weeks of the dosing delay, study treatment may continue at a one-dose-level reduced dose. In participants without biliary obstruction and Grade 4 bilirubin elevation, or with recurrence of Grade 3 bilirubin elevation after a dose reduction, study treatment must be discontinued.

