### **3.0 PARTICIPANT SELECTION**

#### **3.1 Eligibility Criteria**

3.1.1 Participants must have known HIV infection (see [Section 3.1.3](#)) and histologically confirmed solid malignancy that is metastatic or unresectable and for which standard curative or palliative measures do not exist or are no longer effective.

Any number of prior cancer therapies will be permitted. At least 4 weeks must have elapsed since prior chemotherapy or biological therapy, 6 weeks if the regimen included BCNU or mitomycin C. Prior radiation therapy to the thoracic cavity, abdomen, or pelvis must be completed at least 3 months prior to registration; radiotherapy to any other site (including bone or brain metastases) must be completed at least 28 days prior to registration.

3.1.2 Age  $\geq 18$  years on day of consent.

children are excluded from this study.

3.1.3 Serologic documentation of HIV infection at any time prior to study entry, as evidenced by positive ELISA, positive Western blot, or any other federally approved licensed HIV test. Alternatively, this documentation may include a record that another physician has documented that the participant has HIV infection based on prior ELISA and Western blot, or other approved diagnostic tests.

3.1.4 ECOG performance status  $\leq 2$  (Karnofsky  $\geq 60\%$ , see [Appendix II](#)).

3.1.5 Life expectancy of greater than 12 weeks.

3.1.6 Participants must have normal organ and marrow function as defined below within 1 week of study entry:

Leukocytes	$\geq 3,000/\text{mcL}$
Absolute neutrophil count	$\geq 1,500/\text{mcL}$
Platelets	$\geq 100,000/\text{mcL}$
Total bilirubin	$\leq 1.5 \times \text{ULN}$ (If, however, the participant has Gilbert's disease or unconjugated hyperbilirubinemia that is considered to be secondary to atazanavir or indinavir therapy, then the total bilirubin must be $\leq 3 \times \text{ULN}$ )
AST(SGOT)/ALT(SGPT)	$\leq 3.0 \times$ institutional upper limit of normal
Creatinine	$\leq 1.5 \times \text{ULN}$
Creatinine clearance	$\geq 50 \text{ mL/min}/1.73 \text{ m}^2$ for participants with creatinine levels above institutional normal.
Hemoglobin	$\geq 9 \text{ g/dL}$

Serum albumin	$\geq 2.8\text{g/dL}$
Lipase	$<2.0 \times \text{ULN}$ and no radiologic or clinical evidence of pancreatitis
Urine protein/creatinine ratio (UPCR)	$\leq 1$
Serum phosphorus, calcium, magnesium, and potassium	$\geq$ lower limit of normal (LLN)

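### Section 6.1.2 gives only an absolute bilirubin level (<1.5 × ULN) for restarting after a combined hepatic hold, although Section 3.1.6 admits some participants above that level

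*Combined protocol and SAP*

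**What the plan says.** **Entry.** Section 3.1.6 caps total bilirubin at 1.5 × ULN. It raises the cap to 3 × ULN for Gilbert's disease and for "unconjugated hyperbilirubinemia that is considered to be secondary to atazanavir or indinavir therapy, then the total bilirubin must be" within that higher limit.

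**Combined hold.** Section 6.1.2 states: "Cabozantinib treatment should also be interrupted when transaminase increases are accompanied by progressive elevations of total bilirubin, and/or elevations of coagulation tests". The hold lasts until the cause is known and "these abnormalities are corrected or stabilize at clinically acceptable levels". The levels follow in a parenthesis: "clinically acceptable levels (INR < 1.5 × ULN, total bilirubin < 1.5 × ULN, aminotransferases ≤ baseline grade").

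**Neighbouring rules that refer to baseline.**
- The AST/ALT table in Section 6.1.2 is introduced with "Since participants may enter the study with elevations of AST/ALT at baseline, the following guideline should be used for dose modifications".
- For isolated Grade 3 bilirubin, Section 6.1.2 says participants "should have study treatment held until recovered to Grade ≤1 or baseline (or lower").
- The general rule for intolerable Grade 2 events in Table 6-1 reads "If cabozantinib dosing is interrupted, then upon resolution of the AE to baseline or Grade" 1 or lower.

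**Permanent stop.** Section 6.1.2 also says: "Participants must have cabozantinib permanently discontinued if transaminase elevations are accompanied by evidence of impaired hepatic function (bilirubin elevation >2 ×ULN"). This does not apply where there is biliary obstruction or another explanation of the injury.

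**Delay rules.** In Sections 5.2 and 12.1, a Cycle 1 delay of more than 7 days is a DLT. In Sections 5.4 and 6.0, a Cycle 1 delay of 14 days or more ends treatment. Both apply only when the delay is due to unresolved toxicity.

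**The concern.** The plan knowingly admits a group whose bilirubin may sit above 1.5 × ULN for reasons unrelated to cabozantinib. It then gives, as the only bilirubin level for ending one kind of hold, a figure some of them did not meet before their first dose. The same parenthesis makes the aminotransferase criterion relative to baseline, so the omission for bilirubin looks like an oversight.

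The entry elevation is also likely to last through Cycle 1. Section 3.1.9 requires no intention to change the antiretroviral regimen within 8 weeks of entry, and Section 5.3.1.2 permits changes only after 8 weeks. A participant on atazanavir or indinavir would therefore be expected to stay on it throughout the DLT window.

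At stake is whether a participant whose transaminases and INR have recovered, and whose bilirubin is back at its entry value, may resume drug. Two investigators could read the sentence differently. In Cycle 1, the length of the hold affects evaluability and can engage the delay rules.

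**Working it through.** The plan states no figure to reproduce. The check sets its limits side by side.

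**Inputs.** Entry limit under the exception: 3 × ULN (3.1.6). Restart level: below 1.5 × ULN (6.1.2). Permanent-stop figure: above 2 × ULN with transaminase elevation (6.1.2). Cycle length: 28 days of once-daily dosing (5.1). Evaluability: at least 80% of planned dose (5.2). Delay limits: more than 7 days (5.2, 12.1) and 14 days or more (5.4, 6.0).

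**Step 1: who misses the level at their own baseline.** Let b be entry bilirubin in multiples of ULN. Anyone with b ≥ 1.5 who returns exactly to b is not below 1.5. Exception participants who entered below 1.5 are unaffected.

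**Step 2: how far below baseline they must go.** The required fall is more than 1 − 1.5/b.

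| b (× ULN) | 1 − 1.5/b |
|---|---|
| 1.8 | 16.7% |
| 2.0 | 25% |
| 2.5 | 40% |
| 3.0 | 50% |

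**Step 3: where the permanent-stop rule takes over.** A participant with b above 2.0 already meets that rule's bilirubin figure once transaminases rise. One with b = 2.0 meets it on any further bilirubin rise. Unless obstruction or another explanation applies, these participants stop permanently and the restart level is moot. The last two rows are therefore largely theoretical, and the row for 2.0 is the edge. The clearly live range is about 1.5 to 2.0 × ULN.

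**Step 4: which Cycle 1 holds are not already DLTs.** Related Grade 3 ALT is a DLT under 5.2. With normal baseline values, Grade 2 ALT that keeps rising leads to interruption and restart one dose level lower (6.1.2), and a required Cycle 1 reduction is also a DLT. What remains is mainly Grade 1 ALT with a bilirubin or coagulation change. The combined-hold rule itself requires no dose reduction.

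**Step 5: an illustrative case (assumed values).** Entry bilirubin is 1.8 × ULN and ALT is normal. On Day 8 ALT is Grade 1 and bilirubin is 2.0 × ULN, judged progressive but not above the stop figure. Drug is held. After 4 missed doses ALT is normal and bilirubin is back at 1.8.

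| Missed doses | Share of 28 doses | Consequence |
|---|---|---|
| 4 (restart at baseline allowed) | 24/28 = 85.7% | evaluable, no delay DLT |
| 6 | 22/28 = 78.6% | below 80%; may be replaced |
| 8 | 20/28 = 71.4% | past 7 days; DLT only if due to unresolved toxicity |
| 14 | 14/28 = 50% | discontinuation, on the same condition |

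**Step 6: is there a baseline alternative elsewhere?** The isolated-bilirubin rule covers isolated elevations only. Table 6-1 is general guidance, and Section 6.1 sends hepatobiliary disorders to the specific section. Neither clearly supplies a baseline alternative for the combined hold.

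**The case against.** The strongest reply is that the sentence offers two routes. The bracketed figures naturally define the levels at which values may *stabilize*, while *corrected* stands alone. If a progressive bilirubin rise triggered the hold and bilirubin is back at its entry value, that abnormality has been corrected. This stands as a fair reading. It softens the point but does not remove it, because the word is undefined and the only bilirubin figure given is absolute.

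Second, a stricter limit may be deliberate. Transaminases and bilirubin rising together are a more worrying pattern than isolated bilirubin, and the next paragraph treats the combination as a signal of possible severe liver injury. That is a defensible reason for caution. It does not explain why the limit should lie below a value accepted at entry when the aminotransferase limit beside it follows baseline.

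Third, the consequences are limited. Bilirubin at its pre-treatment value is hard to call unresolved toxicity. Replacement below 80% of dose is discretionary. Under Appendix V the Protocol Chair, Medical Monitor and Group Statistician decide whether escalation criteria are met. All of this stands, although central review does not tell a site when to restart drug.

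A reader might infer that everyone admitted at up to 3 × ULN is locked out of restart. The documents do not support that: entry values below 1.5 are unaffected, values above 2 generally fall under another rule, and *corrected* leaves room in between.

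**Conclusion.** The point holds as a minor gap in one restart criterion. Applied as written, the bilirubin figure in Section 6.1.2 keeps a participant who entered at about 1.5 to 2.0 × ULN off drug at a pre-treatment value the plan accepted. In the clear interior case of 1.8 × ULN, the shortfall is a fall of more than 16.7% below baseline. Above 2 × ULN the point matters only where biliary obstruction or another explanation takes the participant out of the permanent-stop rule.

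This rests on the stated figure being enforced despite the word *corrected*, on transaminases and INR having recovered, and on the bilirubin elevation persisting at its entry level. The documents give no frequency for this combination, so none is assumed.

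A reader might infer that the gap inflates the DLT count or biases the MTD. The documents do not support that. A delay counts only if due to unresolved toxicity, the Cycle 1 case is mainly Grade 1 ALT, and escalation criteria are judged centrally. A reader might also conclude that the DLT definition is faulty. It is not: the difficulty lies in the restart level.

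**What to change.** In Section 6.1.2, change the bilirubin restart level to: *total bilirubin < 1.5 × ULN, or at or below the pre-treatment value for participants admitted under the 3 × ULN exception*. Leave unchanged the requirement to determine the etiology, the INR and aminotransferase limits, and the permanent-stop rule.

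No change to Section 5.2 or 12.1 is needed. Once drug may restart at the pre-treatment value, a delay caused only by that value does not arise.

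The cost is one clause. Baseline total bilirubin is already collected under Section 9.1.3, so no new test is required. The downside is a slightly less conservative restart limit in a small subgroup.
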